A central person, independent from the study, with access to the randomisation list and the eCRF for the MIV-711-201 study will confirm Inclusion Criterion 1. The confirmation will be communicated to the site staff and the study team via fax/email without revealing the treatment in MIV-711-201 or the change in NRS score.

All enrolled patients will receive 200 mg q.d. oral dose of MIV-711 for 26 weeks in addition to their current medication. MIV-711 200 mg will be provided as identical capsules to those used in Study MIV-711-201.

The patients will take the last dose of IMP in Study MIV-711-201 at Visit 8 and dosing in the present study will be started at Visit 2 after a screening period of  $10 \pm 5$  days.

Patients who are not eligible to participate in the present study will return for the safety follow up visit (Visit 9) in Study MIV-711-201.

Patients will be permitted to remain on their current analgesic regimen with any changes in concomitant medications reported and recorded at study visits as well as in a patient-reported daily e-diary for two 2-week periods prior to Visit 4 and Visit 5.

The study consists of a Screening period of approximately 2 weeks (Visit 1), eligibility at Visit 2, an open-label treatment period of 26 weeks from Visit 2 through Visit 5, and a follow-up period of 4 weeks (Visit 6) after the last dose of study treatment is administered. Telephone calls will be made 5-9 days after all dosing visits for safety and tolerability. There will be additional phone calls at Week 10 and Week 20 for safety and tolerability.

A Data Monitoring and Ethics Committee will meet to review the unblinded safety and tolerability data after the first 25 patients complete Visit 4 and Visit 5.

Treatment	All patients will receive a 200 mg oral dose of MIV-711 q.d. for 26 weeks in addition to their current medication.
Number of Patients	All patients in Study MIV-711-201 at the participating sites included in Study MIV-711-202 will be given the opportunity to participate provided that they meet the eligibility criteria. However, based on the inclusion and exclusion criteria it is anticipated that 50-80 patients will be eligible for participation. The patients will be recruited from up to 5 centres in up to 5 countries for this study.

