No clinically meaningful effects on vital signs, laboratory parameters or electrocardiogram (ECG) time intervals: including QTc interval (Fridericia's correction; QTcF) were observed. Adverse events (AEs) assessed as related to investigational medicinal product (IMP) had a similar incidence for active treatment and for placebo. One subject was found on a per protocol ECG to have asymptomatic atrial fibrillation after 3 q.d. doses of MIV-711 200 mg. Spontaneous conversion to sinus rhythm occurred within 24 hours after the last dose. Investigations by an independent cardiologist supported that the post-dose atrial fibrillation observed was possibly drug induced. Further details of the results of the FTIM study are provided in the IB.

The ongoing MIV-711-201 study, from which the patients in the current protocol will be recruited, will include 240 patients under 1:1:1 randomisation to placebo: 100 mg MIV-711: 200 mg MIV-711. The first patient was randomised in March 2016 and recruitment is ongoing; as of 21 June 2016, 102 patients have been enrolled. No treatment-related serious adverse events (SAEs) have been reported to date. One unrelated SAE was reported before the start of dosing. Seven patients were withdrawn from the study due to the following reasons: increased liver function tests; severe polymyalgia; suspected macular-papular rash; angioedema; non-compliance; lost to follow-up; withdrawal of consent. No safety-related trends have been identified in the ongoing Study MIV-711-201 and it is believed that MIV-711 has acceptable safety and tolerability based on blinded results in OA patients.

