### 3 STUDY OBJECTIVES

#### 3.1 Primary Objective Study Population A\*

To assess the safety and tolerability of 200 mg MIV-711 q.d. over 52 (26+26) weeks in patients with symptomatic and radiographic knee osteoarthritis.

\* Study Population A will be recruited from patients treated with 200 mg MIV-711 q.d. in Study MIV-711-201 and whose symptoms did not clinically significantly deteriorate as defined by an increase in NRS of  $\leq 2$  compared to Baseline.

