### 5.1 Inclusion Criteria

Patients must meet all of the following criteria to be eligible for enrolment in this study:

1. Previously enrolled in Study MIV-711-201 including completion of Visit 8 either by
  - Receiving MIV-711 200 mg and had non-significant clinical worsening on the primary endpoint as defined by NRS increase of  $\leq 2$

OR by

- Receiving placebo and had a clinically significant worsening on the primary endpoint as defined by NRS increase of  $\geq 2$

The NRS result will be derived using the primary endpoint from Study MIV-711-201: NRS average knee pain in the target knee with 7 days recall: increase from Baseline (Visit 2 of Study MIV-711-201) to Visit 8 of Study MIV-711-201.

2. Female patients must be non-pregnant, non-lactating and of non-childbearing potential either as naturally (spontaneously) post-menopausal or due to hysterectomy and/or bilateral oophorectomy/salpingo-oophorectomy (as determined by patient medical history). Naturally (spontaneously) post-menopausal is defined as being amenorrhoeic for 12 months without an alternative medical cause and with a Screening follicle stimulating hormone test indicating post-menopausal state.
3. Male patients should avoid fathering a child by either of the following methods:
  - True sexual abstinence: meaning that heterosexual abstinence is in line with the preferred and usual lifestyle of the patient (periodic abstinence such as that based on calendar, ovulation, symptothermal, post-ovulation methods, declaration of abstinence for the duration of a trial, or withdrawal/coitus interruptus are not acceptable methods of contraception).
  - Willingness to use two effective means of contraception with their partner from the time of first IMP administration until 3 months after the last dose of IMP. Two or more of the following methods are acceptable and must include at least one barrier method: i) Surgical sterilisation (i.e., bilateral tubal ligation for female partners; vasectomy for male), ii) placement of an intrauterine device or intrauterine system, iii) hormonal contraception (implantable, patch, oral), iv) barrier methods including condom or occlusive cap (diaphragm or cervical/vault caps) with spermicidal foam/gel/film/cream/suppository. Male patients who have been sterilised are required to use one barrier method of contraception (condom).

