## 5.2 Exclusion Criteria

Patients will be excluded from enrolment in this study if they meet any of the following criteria:

1. The presence of any inflammatory arthritis (e.g., gout, reactive arthritis, rheumatoid arthritis, psoriatic arthritis, seronegative spondylarthropathy) or any underlying condition, other than OA, that may result in abnormal cartilage and bone metabolism.
2. Any generalised pain condition that may interfere with the evaluation of the target knee pain (e.g., fibromyalgia) as judged by the investigator.
3. Ongoing or a history of atrial fibrillation.
4. Currently receiving medication that affects cartilage or bone metabolism (other than study drug; hormone replacement therapy taken for more than 6 months is allowed).
5. Current or recurrent disease that could affect the action, absorption or disposition of MIV-711, or could affect clinical assessments or clinical laboratory assessments.
6. Any clinically severe or significant uncontrolled concurrent illness, which, in the opinion of the Investigator, would impair ability to give informed consent or take part in or complete this clinical study.
7. Any medical condition, AE, clinical or laboratory finding from Study MIV-711-201 that, in the opinion of the Investigator, would preclude inclusion in the present clinical study.
8. Known or suspected intolerance or hypersensitivity to the investigational medicinal product, closely related compounds, or any of the stated ingredients.
9. History of alcohol or other substance abuse within the last year.
10. Use of an investigational product other than MIV-711 during participation in Study MIV-711-201 and /or active enrolment in another drug or vaccine clinical study.
11. Significant target knee injury or surgery during participation in Study MIV-711-201.
12. A history of partial or complete joint replacement surgery in the target knee at any time, listed for knee surgery, or anticipating knee surgery during the study period.
13. Any factor which, in the opinion of the investigator, would jeopardise the evaluation or safety of the patient or be associated with poor adherence to the clinical study protocol (e.g., inability to complete study diary, poor tolerability of venepuncture or lack of adequate venous access for required blood sampling during the study period).
14. Use of intra-articular hyaluronic acid in the target knee during participation in Study MIV-711-201.

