- Number and Percentage of Patients with Treatment Emergent Adverse Events ‘Related to IMP’ by System Organ Class, Preferred Term, and Severity.
- Number and Percentage of Patients with Serious Treatment Emergent Adverse Events by System Organ Class, and Preferred Term
- Number and Percentage of Patients with Treatment Emergent Adverse Events Leading to Discontinuation by System Organ Class, and Preferred Term
- Number and Percentage of Patients with Treatment Emergent Adverse Events by Preferred Term per Frequency of Occurrence

All AE summary tables will display the AEs that occurred in both MIV-711-201 and MIV-711-202 studies for patients that were dosed in MIV-711-202. For tabulations of AEs by study group, any AE that starts on or after administration of the first dose received in MIV-711-201 and before the first dose received in MIV-711-202, will be assigned to the the 201 study group. Any AE occurring after the first dose administered in MIV-711-202 will be assigned to the 202 study group.

If a subject has multiple AEs with the same preferred term but occurring after each dose administration (MIV-711-201 and MIV-711-202), then one AE will be counted for each treatment administration. Adverse events that emerge in the first treatment period (201) and carry over into the next period (202) will be attributed to only the period in which the AE emerged (201). Such AEs that carry over into MIV-711-202 will be recorded as part of MIV-711-202 medical history.

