Number and Percentage of Patients with Treatment Emergent Adverse Events Leading to Discontinuation
by System Organ Class, Preferred Term, and Group
SAF Population

System Organ Class Preferred Term	MIV-711-201			MIV-711-202		
	Group A 26 weeks N = x	Group B 26 weeks N = x	Overall N = x	Group A 26 weeks N = x	Group B 26 weeks N = x	Overall N = x
System Organ Class 1	nn (nn.n%)	nn (nn.n%)	nn (nn.n%)	nn (nn.n%)	nn (nn.n%)	nn (nn.n%)
Preferred Term 1	nn (nn.n%)	nn (nn.n%)	nn (nn.n%)	nn (nn.n%)	nn (nn.n%)	nn (nn.n%)
Preferred Term 2	nn (nn.n%)	nn (nn.n%)	nn (nn.n%)	nn (nn.n%)	nn (nn.n%)	nn (nn.n%)
Preferred Term 3	nn (nn.n%)	nn (nn.n%)	nn (nn.n%)	nn (nn.n%)	nn (nn.n%)	nn (nn.n%)
Preferred Term xx	nn (nn.n%)	nn (nn.n%)	nn (nn.n%)	nn (nn.n%)	nn (nn.n%)	nn (nn.n%)
System Organ Class 2	nn (nn.n%)	nn (nn.n%)	nn (nn.n%)	nn (nn.n%)	nn (nn.n%)	nn (nn.n%)
Preferred Term 1	nn (nn.n%)	nn (nn.n%)	nn (nn.n%)	nn (nn.n%)	nn (nn.n%)	nn (nn.n%)
Preferred Term 2	nn (nn.n%)	nn (nn.n%)	nn (nn.n%)	nn (nn.n%)	nn (nn.n%)	nn (nn.n%)
Preferred Term 3	nn (nn.n%)	nn (nn.n%)	nn (nn.n%)	nn (nn.n%)	nn (nn.n%)	nn (nn.n%)
Preferred Term xx	nn (nn.n%)	nn (nn.n%)	nn (nn.n%)	nn (nn.n%)	nn (nn.n%)	nn (nn.n%)

PAREXEL International SAP Amendment Shells

Medivir
Protocol: MIV-711-202

Final 1.0
16 January 2018

Medivir
Protocol Number: MIV-711-202

Page X of Y

Table 14.3.1.6
Number and Percentage of Patients with Treatment Emergent Adverse Events by Frequency, Preferred Term, and Group
SAF Population

	MIV-711-201			MIV-711-202		
	Group A 26 weeks N = x	Group B 26 weeks N = x	Overall N = x	Group A 26 weeks N = x	Group B 26 weeks N = x	Overall N = x
Preferred Term						
Preferred Term 1	nn (nn.n%)	nn (nn.n%)	nn (nn.n%)	nn (nn.n%)	nn (nn.n%)	nn (nn.n%)
Preferred Term 2	nn (nn.n%)	nn (nn.n%)	nn (nn.n%)	nn (nn.n%)	nn (nn.n%)	nn (nn.n%)
Preferred Term 3	nn (nn.n%)	nn (nn.n%)	nn (nn.n%)	nn (nn.n%)	nn (nn.n%)	nn (nn.n%)
Preferred Term xx	nn (nn.n%)	nn (nn.n%)	nn (nn.n%)	nn (nn.n%)	nn (nn.n%)	nn (nn.n%)

PAREXEL International SAP Amendment Shells

Medivir
Protocol: MIV-711-202

Final 1.0
16 January 2018

Medivir
Protocol Number: MIV-711-202

Page X of Y

Table 14.3.2.1
Clinical Laboratory Chemistry - Summary of Observed Values
SAF Population

Lab Parameter = *Lab Parameter (unit)*

Visit	Statistic	Group A N = x	Group B N = x
	n	nn	nn
VISIT 1	Mean	xx.x	xx.x
MIV-711-201	SD	xx.xx	xx.xx
	Median	xx.x	xx.x
	Min	xx	xx
	Max	xx	xx
	n	nn	nn
VISIT 2	Mean	xx.x	xx.x
MIV-711-201	SD	xx.xx	xx.xx
	Median	xx.x	xx.x

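### The weeks 0–26 adverse-event columns for Group A describe only 200 mg patients who completed Study 201 and rolled over, and no output shows the rest or labels the figures as conditional

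*SAP*

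**What the plan says.** The primary objective (Protocol 3.1) is: "To assess the safety and tolerability of 200 mg MIV-711 q.d. over 52 (26+26) weeks in patients with symptomatic and radiographic knee osteoarthritis". For Group A, the first 26 of those weeks are Study 201 and the second 26 are Study 202.

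Entry to Group A is set in the Protocol:

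- Section 5.1, criterion 1: "Previously enrolled in Study MIV-711-201 including completion of Visit 8 either by" one of two routes. The Group A route is "Receiving MIV-711 200 mg and had non-significant clinical worsening on the primary endpoint as defined by NRS increase of" at most 2.
- Visit 8 is the end-of-treatment visit of Study 201. From the synopsis: "The patients will take the last dose of IMP in Study MIV-711-201 at Visit 8".
- Section 5.2, criterion 7, excludes for "Any medical condition, AE, clinical or laboratory finding from Study MIV-711-201 that, in the opinion of the Investigator, would preclude inclusion". This is investigator judgement, not a fixed list. Criterion 3 separately excludes current or past atrial fibrillation.

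The SAP then fixes who is counted. Sections 4.6.1 and 4.6.3 make the safety set the same as the ITT set, meaning at least one dose in Study 202. Section 9.1 adds: "All AE summary tables will display the AEs that occurred in both MIV-711-201 and MIV-711-202 studies for patients that were dosed in MIV-711-202". The listing of Study 201 events carries the same limit.

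The table shells nevertheless print a Study 201 block with a 26-week Group A column. In Table 14.3.1.1 it has rows for deaths and for events leading to early discontinuation. In Table 14.3.1.5 it reports "Number and Percentage of Patients with Treatment Emergent Adverse Events Leading to Discontinuation".

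**The concern.** Safety and tolerability is the only primary objective and the analysis is purely descriptive, so denominators and labels carry the whole result. A 200 mg patient who stopped in week 6 of Study 201 because of an adverse event and left the study is in neither the numerator nor the denominator of the Study 201 Group A column. The patients who remain were chosen partly for having tolerated 26 weeks of the drug.

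The shells of Tables 14.3.1.1 to 14.3.1.6 carry no note of this. Someone who reads the Study 201 and Study 202 columns together as the 26+26-week record would take the first column as an estimate of tolerability on 200 mg from the start of treatment, which it is not.

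**Working it through.** **Who can appear in the Study 201 Group A column**

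1. To be counted, a patient must be dosed in Study 202 (SAP 4.6.1, 4.6.3 and 9.1).
2. To be dosed in Study 202 through the Group A route, a patient must have completed Visit 8 of Study 201, have an NRS increase of at most 2, and pass the exclusions (Protocol 5.1 and 5.2).
3. So no death before Visit 8, and no exit from Study 201 before Visit 8, can appear.
4. Events at or before Visit 8 that the investigator judged to preclude entry are also absent, as is any patient with recognised atrial fibrillation. Protocol 2.2 reports one case of atrial fibrillation at 200 mg in the first-in-man study, considered possibly drug induced.

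**What can still appear in the discontinuation rows**

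SAP 9.1 assigns events by onset. An event that starts after the first Study 201 dose and before the first Study 202 dose goes to the Study 201 column, even if it carries over. An event that began in Study 201, or in the 10±5-day gap, and led to withdrawal in Study 202 would therefore fall in the Study 201 column. A patient who stopped drug but still attended Visit 8 might also qualify; the Study 201 protocol is not supplied, so this cannot be settled. The row is not guaranteed to be zero, but carry-over entries of this kind are not stops in weeks 0–26.

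**Other outputs**

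- *Laboratory shifts (Tables 14.3.2.3 to 14.3.2.6).* SAP 9.2.1 takes the minimum and maximum over all visits after baseline. For Group A these run across both studies, so the same selection enters a single cumulative figure. The shells footnote the unequal number of visits between groups, but not the selection.
- *Disposition (Table 14.1.1).* This starts at enrolment in Study 202. No output counts the 200 mg patients who did not roll over, or says why.

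**Size**

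The documents give no sample-size or power figure to reproduce, and no count of early stoppers on 200 mg.

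- 200 mg arm of Study 201: 240 patients randomised 1:1:1 (Protocol 2.2), so 240/3 = 80.
- Blinded withdrawals at 21 June 2016, all arms (Protocol 2.2): "Seven patients were withdrawn from the study due to the following reasons: increased liver function tests; severe polymyalgia; suspected macular-papular rash; angioedema", plus three for non-compliance, loss to follow-up and withdrawn consent. Total 7/102 = 6.9% (exact 95% CI 2.8–13.6%). The four medical reasons give 4/102 = 3.9% (1.1–9.7%).
- The first patient was randomised in March 2016. From 1 March to 21 June is 112 days, or 16 weeks, so nobody had reached week 26.
- Assume that a fraction d of the 80 stops early for an adverse event. With d = 4%, 0.04 × 80 = 3.2; with d = 10%, 0.10 × 80 = 8. That is roughly 3 to 8 patients.
- With d = 5%, the chance of at least one such patient is 1 − 0.95^80 = 98.3%.
- Effect on the any-event percentage: if completers have incidence q and every early stopper has an event, the full-arm figure is d + (1 − d)q, which exceeds q by d(1 − q). With q assumed at 30–50%, this is 2.5–3.5 percentage points at d = 5% and 5–7 points at d = 10%.

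**The case against.** The strongest reply has four parts.

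- *An extension can only follow patients who roll over, and the plan says so.* The Protocol abstract speaks of a subset of the study population, section 3.1 defines Population A directly under the objective, and SAP 9.1 states the restriction plainly. This stands: the selection is not an error of design and is not concealed. But the disclosure is not in the tables, and none of these places says that early stopping on 200 mg cannot be seen.
- *The adverse-event tables show two labelled 26-week blocks, not a pooled 52-week percentage.* This also stands. The problem is the content of the Study 201 block and any 26+26 reading of it. The laboratory shift tables, however, do span both studies.
- *Study 201 is a separate randomised trial and may report its full 200 mg arm.* It may. The documents do not describe that report, so the data are not shown to be lost. Equally, this plan neither presents those figures nor refers to them.
- *The available withdrawal data are weak.* Agreed. They are blinded, pooled over placebo, 100 mg and 200 mg, immature, and based on enrolled patients; they do not say whether the withdrawals occurred on drug.

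A reader might go further and infer that the Study 201 discontinuation rows are zero by design. The onset rule in SAP 9.1 rules that out. A reader might also subtract an assumed Group A size of 40–60 from 80 and conclude that 25–50% of the arm was lost to early stopping. That count would mix in patients with an NRS increase above 2, at non-participating sites, who declined, or without a Visit 8 MRI, many of whom may have completed 26 weeks. In addition, the forecast of 50–80 patients is for Groups A and B together.

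**Conclusion.** The point holds as one of reporting and interpretation. The Study 201 Group A columns cannot include a death or an exit before Visit 8, and they are likely to understate serious, severe and treatment-stopping events on 200 mg in weeks 0–26. Patients removed by those events, or kept out because of them, are not counted. The exclusion of deaths and exits before Visit 8 follows directly from the entry criteria and SAP 9.1. The understatement of other events is an expectation about direction, not a measured bias.

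Its size cannot be taken from the documents. About 3 to 8 omitted patients rests on an assumed 4–10% early-stop rate for adverse events in an arm of about 80; the blinded 4/102 is only a rough guide to that rate. As planned, Group A supports a statement about 52 weeks of treatment in patients who reached week 26 and rolled over. It does not support an unconditional statement about 52 weeks of 200 mg in patients with knee osteoarthritis.

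**What to change.** 1. In SAP 9.1 and Tables 14.3.1.1 to 14.3.1.6, add to the Study 201 block a column for all patients treated with 200 mg in Study 201, taken from that study's safety set. At minimum, present those adverse-event, SAE, death and discontinuation figures alongside. Use them for any statement about weeks 0–26.
2. Add a count running from randomised to 200 mg in Study 201 to dosed in Study 202, with reasons for not rolling over.
3. Footnote the Group A Study 201 columns, and the Group A laboratory shift tables that span both studies, as conditional on completing Visit 8 and rolling over, so that deaths and withdrawals from Study 201 before Visit 8 cannot appear. The footnote should not say that discontinuations are zero by design.
4. Word the 52-week conclusion as applying to patients who completed 26 weeks of Study 201 on 200 mg without clinically significant worsening and rolled over.

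The cost is SAP wording, one column in six tables, one flow count and some footnotes. It uses existing Study 201 data and needs no new patients or procedures. The drawbacks are that the added column includes Study 201 sites that did not take part in Study 202, and that the rates will probably look less favourable.

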4.4 Safety Variables

4.4.1 Adverse Events

All AEs and SAEs will be recorded in the eCRF system from the date the informed consent form is signed (visit 1) until the safety follow up visit (visit 6) is completed.

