9.1 Adverse Events

All AEs reported will be coded and classified according to MedDRA version 18.1. A treatment-emergent AE (TEAE) will be defined as an AE that begins or that worsens in severity after IMP has been administered.

Non-treatment emergent adverse events (NTEAE): AEs that occurred before the administration of IMP and did not worsen in severity or relationship after exposure to IMP.

All AE data as captured on the CRF for MIV-711-202 study will be listed by patient. All AEs from MIV-711-201 study for those patients admitted into the MIV-711-202 study will also be listed. All serious AEs (SAEs) will be listed. A listing of all AEs leading to treatment discontinuation will be presented.

Unless specified otherwise, all adverse event summaries will include the TEAEs only and adverse event summary counts of AEs will be the number of patients reporting adverse events and not the number of events reported. The number and percentage of patients with adverse events will be tabulated by body system (SOC) and preferred term (PT) for each group (A, B) and study (MIV-711-201, MIV-711-202). A patient with multiple adverse events within a body system is only counted once towards the total of that body system. If the same AE (preferred term) is reported several times for the same patient, it will only appear once for that specified treatment in the summary tables.

For patients with multiple adverse events of the same preferred term and of different severities, the AE with the highest assessment of severity will be used in the summaries presented by severity.

A general summary of all treatment-emergent adverse events will show the number and percentage of patients, as well as the number of events, according to the following categories:

- All treatment emergent adverse events
- ‘Related’ treatment emergent adverse events
- Mild treatment emergent adverse events
- Moderate treatment emergent adverse events
- Severe treatment emergent adverse events
- Serious treatment emergent adverse events
- Treatment emergent adverse events leading to early termination
- Deaths

Other summary tables for adverse events will include:

PAREXEL International Statistical Analysis Plan

Medivir
Protocol: MIV-711-202

Final 1.0
16 January 2018

- Number and Percentage of Patients with Treatment Emergent Adverse Events by System Organ Class, and Preferred Term

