
PAREXEL International SAP Amendment Shells

Medivir
Protocol: MIV-711-202

Final 1.0
16 January 2018

Medivir
Protocol Number: MIV-711-202

Page X of Y

Table 14.2.8.3
Brief Medication Questionnaire - Number and Percentage of Patients with each Medication by Indication and Visit
PPS Population

Medication	Visit	Group A N = x	Group B N = x
	Indication 1	nn (nn.n%)	nn (nn.n%)
		nn (nn.n%)	nn (nn.n%)
		nn (nn.n%)	nn (nn.n%)
	Indication 2	nn (nn.n%)	nn (nn.n%)
		nn (nn.n%)	nn (nn.n%)
		nn (nn.n%)	nn (nn.n%)
	Etc..		

PAREXEL International SAP Amendment Shells

Medivir
Protocol: MIV-711-202

Final 1.0
16 January 2018

Medivir
Protocol Number: MIV-711-202

Page X of Y

Table 14.2.8.4
Brief Medication Questionnaire - Compliance
Number and Percentage of Patients Who Missed Taking their Medication by Visit
ITT Population

Medication Name	How many times did you miss taking it?	Visit	Group A N = x	Group B N = x
	0		nn (nn.n%)	nn (nn.n%)
	1		nn (nn.n%)	nn (nn.n%)
	2		nn (nn.n%)	nn (nn.n%)
	3			
	Etc..			

PAREXEL International SAP Amendment Shells

Medivir
Protocol: MIV-711-202

Final 1.0
16 January 2018

Medivir
Protocol Number: MIV-711-202

Page X of Y

Table 14.3.1.1
Summary of Treatment Emergent Adverse Events
SAF Population

	MIV-711-201			MIV-711-202		
	Group A 26 weeks N = x	Group B 26 weeks N = x	Overall N = x	Group A 26 weeks N = x	Group B 26 weeks N = x	Overall N = x
All AEs	nn (nn.n%) E	nn (nn.n%) E	nn (nn.n%) E	nn (nn.n%) E	nn (nn.n%) E	nn (nn.n%) E
'Related' AEs	nn (nn.n%) E	nn (nn.n%) E	nn (nn.n%) E	nn (nn.n%) E	nn (nn.n%) E	nn (nn.n%) E
Mild AEs	nn (nn.n%) E	nn (nn.n%) E	nn (nn.n%) E	nn (nn.n%) E	nn (nn.n%) E	nn (nn.n%) E
Moderate AEs	nn (nn.n%) E	nn (nn.n%) E	nn (nn.n%) E	nn (nn.n%) E	nn (nn.n%) E	nn (nn.n%) E
Severe AEs	nn (nn.n%) E	nn (nn.n%) E	nn (nn.n%) E	nn (nn.n%) E	nn (nn.n%) E	nn (nn.n%) E
Deaths	nn (nn.n%) E	nn (nn.n%) E	nn (nn.n%) E	nn (nn.n%) E	nn (nn.n%) E	nn (nn.n%) E
Serious AEs	nn (nn.n%) E	nn (nn.n%) E	nn (nn.n%) E	nn (nn.n%) E	nn (nn.n%) E	nn (nn.n%) E
AEs Leading to early discontinuation from study	nn (nn.n%) E	nn (nn.n%) E	nn (nn.n%) E	nn (nn.n%) E	nn (nn.n%) E	nn (nn.n%) E

TEAE = Treatment Emergent Adverse Event
 nn = Number of Patientswith TEAEs
 N = Number of PatientsExposed
 (nn.n%) = nn/N x 100
 E = Number of AEs

PAREXEL International SAP Amendment Shells

Medivir
Protocol: MIV-711-202

Final 1.0
16 January 2018

Medivir
Protocol Number: MIV-711-202

Page X of Y

Table 14.3.1.2

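### The adverse-event tables count about 27 weeks in study 201 and 30 weeks in study 202, but head every group column 26 weeks

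*SAP*

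**What the plan says.** SAP 9.1 defines a treatment-emergent event as "an AE that begins or that worsens in severity after IMP has been administered". It sets no end date, and neither does the definition in Protocol 7.13.1.

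For tabulation, SAP 9.1 gives to study 201 "any AE that starts on or after administration of the first dose received in MIV-711-201 and before the first dose received in MIV-711-202". For study 202 the rule is: "Any AE occurring after the first dose administered in MIV-711-202 will be assigned to the 202 study group". Neither rule refers to the last dose. SAP 4.4.1 has events recorded "from the date the informed consent form is signed (visit 1) until the safety follow up visit (visit 6) is completed", so the 202 window closes in practice at Visit 6.

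The shells for Tables 14.3.1.1 to 14.3.1.6 (SAP section 14) place a 201 block beside a 202 block. Within each block the group columns carry a duration, as in "Group A 26 weeks N = x", and the Overall column carries none. The legend to Table 14.3.1.1 gives the denominator as "N = Number of PatientsExposed". No shell states the counting window, gives person-time, or separates events on drug from events after stopping.

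**The concern.** AE incidence is the first-listed primary safety endpoint (Protocol 7.1), and the primary objective ties it to 26+26 weeks of dosing in Group A. These tables are the main AE summary. A reader who sees one 26-week heading over both blocks will take them as equal windows and will compare early with later treatment in Group A, or placebo with active drug in Group B.

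The windows are unequal, and they contain different amounts of off-drug time: about 10 days in 201 and 28 days in 202. On the nominal schedule the longer window always falls on 202, so a constant event rate would show a slightly higher percentage there. An event that arises only after stopping the drug would also sit in a column headed 26 weeks, with nothing in the summary table to mark it.

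The SAP deals with the same issue for laboratory data. SAP 9.2.1 describes the post-baseline extremes as taken over visits on drug, and the laboratory shift tables carry a note that the number of visits differs between groups. The AE tables have neither.

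**Working it through.** **Inputs**
- Dosing of 26 weeks in 202 (SAP 3.5), with Visit 5 at day 182, Visit 6 at day 210 ± 7, and the last dose at Visit 5 (SAP 4.2 and note I).
- Last 201 dose at Visit 8, week 26 ± 7 days (SAP 4.1 and note I).
- First 202 dose after a screening period of 10 ± 5 days (Protocol 4 and 8.1).
- Terminal half-life of 3.3 to 5.2 hours (Protocol 2.2).

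**Step 1: reproduce the heading.** 182 / 7 = 26.0 weeks. The heading matches the planned dosing duration.

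**Step 2: the 201 counting window.** This is 182 days plus the gap.
- Gap 5 days: 187 days = 26.7 weeks, 2.7% over 182 days.
- Gap 10 days: 192 days = 27.4 weeks, 5.5% over.
- Gap 15 days: 197 days = 28.1 weeks, 8.2% over.

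**Step 3: the 202 counting window.** 210 / 7 = 30.0 weeks, and 210 / 182 = 1.154, or 15.4% over. The off-drug share is 28 / 210 = 13.3%.

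**Step 4: are the tails really off drug?** The shortest gap is 5 × 24 = 120 hours, and 120 / 5.2 is about 23 half-lives. Pharmacokinetically, yes.

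**Step 5: ratio of the windows.** 210 / 192 = 1.09, with a range from 210 / 197 = 1.07 to 210 / 187 = 1.12. The difference is 13 to 23 days, nominally 18. Allowing ± 7 days at Visit 8 and at Visit 6, the 201 window runs from 175 + 5 = 180 to 189 + 15 = 204 days and the 202 window from 203 to 217. The ratio then spans 203 / 204 = 1.00 to 217 / 180 = 1.21.

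**Step 6: effect on a percentage.** The documents give no event rates, so the 26-week risk p is assumed, with a constant hazard on and off drug: p(d) = 1 − (1 − p)^(d/182).

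| Assumed 26-week risk | 201 block, 192 days (187 to 197) | 202 block, 210 days | 202 minus 201, points (range over the gap) |
|---|---|---|---|
| 10% | 10.5% (10.3 to 10.8) | 11.4% | 0.9 (0.7 to 1.2) |
| 20% | 21.0% (20.5 to 21.5) | 22.7% | 1.7 (1.2 to 2.2) |
| 50% | 51.9% (50.9 to 52.8) | 55.1% | 3.2 (2.3 to 4.1) |

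**Step 7: scale against sampling error.** The 95% half-width of one percentage is 1.96 × √(p(1 − p)/n). At p = 20% it is 14.3 points for n = 30, 11.1 for n = 50 and 8.8 for n = 80. Group sizes are not stated. The protocol expects 50 to 80 patients over both groups, so 30 to 80 is an assumed range. This is a yardstick for a single percentage. The error of a within-patient difference depends on a correlation that the documents do not give.

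**The case against.** The strongest reply is that the heading is not wrong. It gives the planned dosing duration, which SAP section 3 keeps apart from the 4-week follow-up, and the percentage is defined simply as patients with events over patients exposed. A reader might infer that the table misstates exposure; the documents do not support that. Nor is counting into a protocol-specified safety follow-up an error in itself. Both replies stand. What they leave open is that the heading is the only duration shown, and it is not the period over which events are counted.

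A reader might also infer that off-drug events can no longer be told apart. That goes too far. Listings 16.2.7.1 to 16.2.7.3 give start and stop dates and time from first dose, and Listing 16.2.5.2 gives dosing dates at clinic visits. For completers, a post-treatment event can be identified. Only the summary tables lack the split.

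On size, no safety test is planned (Protocol 9.5.4), the shift is 1 to 3 points nominally, and visit windows can remove the difference altogether. Events carried over from 201 are counted only in 201 (SAP 9.1), which pulls the 202 counts down, so the net direction of a 202-versus-201 comparison is not fixed. The constant-hazard figures may also overstate the effect for drug-related events, given the short half-life. All of this stands and keeps the point modest.

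Finally, a cut at last dose is imperfect. SAP 7.9 says the last dose date is not captured for withdrawn patients. The withdrawal date may fall later than the last dose, because patients who stop drug are still asked to attend Visit 6. An event one day after Visit 5 would move to follow-up. A single off-drug column would mix post-placebo and post-active time in Group B. These are reasons to design the split with care and to keep the uncut counts beside it.

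**Conclusion.** The point holds as one of unequal, undisclosed counting windows. On the nominal schedule the 201 block covers 26.7 to 28.1 weeks and the 202 block about 30, under one 26-week heading that describes dosing only. The primary AE percentages are therefore not like-for-like across blocks, and the summary tables merge on-drug with off-drug events.

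The window lengths rest on nominal visit days. Patients who withdraw have shorter windows, and the gap can exceed 15 days if Visit 8 and Visit 1 fall on different days. The size, 1.7 points at a 20% risk, rests on the constant-hazard assumption and lies within sampling error for groups of this order.

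A reader might go further and infer that the two halves cannot be compared, or that an apparent rise in 202 would be an artefact. The documents do not support either: the window difference is about 9% nominally, no comparison of the halves is tested, and the carry-over rule works the other way. The case for change is that the real windows and the split can be shown at little cost for the primary endpoint, largely from data already held.

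**What to change.** In SAP 9.1 and the shells for Tables 14.3.1.1 to 14.3.1.6:

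1. Keep the all-TEAE counts, and label each block with its actual window: first 201 dose to first 202 dose (nominally 27.4 weeks, range 26.7 to 28.1), and first 202 dose to Visit 6 (nominally 30 weeks).
2. In Tables 14.3.1.1, 14.3.1.2 and 14.3.1.4, add a split by AE onset, by group: on-treatment 201, between-study gap, on-treatment 202, and post-202 follow-up. Keep the gap and the follow-up in separate columns, because Group B's gap follows placebo.
3. Reserve the 26-week heading for the on-treatment columns.
4. For withdrawn patients, use the withdrawal date as the end of treatment and footnote the approximation.

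The cost is SAP wording, added columns in three tables, slightly smaller on-treatment percentages, and an approximate cut for withdrawn patients. No new data collection is needed, and no event leaves the tables because the all-TEAE counts remain.
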